4.4.1.2.5 Duration

Duration is derived from the start and end dates of the unsolicited AE:

Duration = End date of unsolicited AE - start date of unsolicited AE + 1.

The duration is considered as missing only if one or both of the start and end dates of the unsolicited AE is missing or partially missing.

-
- Confidential/Proprietary Information
 - Page 50 of 67

4.4.1.3 Serious Adverse Events

An event will be considered as a serious event if “Yes” is checked for “Serious” in the CRF.

SAEs will be analyzed throughout the study using the following periods:

- Within 7 days after vaccination
- Within 30 days after vaccination
- During the study (i.e., all SAEs occurred during the study)

4.4.1.4 Adverse Events of Special Interest

An event will be considered as an AESI if “Yes” is checked for “Is the event an AESI?” in the CRF.

AESIs will be analyzed throughout the study using the following periods:

- Within 7 days after vaccination
- Within 30 days after vaccination

During the study (i.e., all SAEs occurred during the study)

4.4.1.5 Other Safety Endpoints

4.4.1.5.1 Action Taken

This information will be summarized as collected, including missing observations. No derivation or imputation will be done.

4.4.1.5.2 Seriousness

This information will be summarized as collected for SAEs. No derivation or imputation will be done.

4.4.1.5.3 Outcome

This information will be summarized as collected for Unsolicited non-serious AEs and SAEs. No derivation or imputation will be done.

4.4.1.5.4 Causal relationship

By convention, all events reported at the injection site (either solicited or unsolicited) will be considered as related to the administered product and then referred to as reactions. In a same way, all solicited systemic events pre-listed in

-
- Confidential/Proprietary Information
 - Page 51 of 67

the CRF are also considered as related to vaccination and will be considered as reactions.

- For unsolicited systemic AE, missing relationship to IMP will be considered as related to study vaccines at the time of analysis.
- The missing relationship to study procedures for SAEs will not be imputed.

4.4.1.5.5 Adverse Events Leading to Study Discontinuation

This information will be summarized as collected. A flag is available in the clinical database for all AEs in order to identify AEs leading to discontinuation before the end of active phase.

In general, the items that are counted are:

- Disposition table: A participant who, on the “Completion at End of Study” form question “What was the participant's status?” has “Adverse Event” checked.
- Safety overview table: A participant who has either on the “Completion at End of Study” form, question “What was the participant's status?” has “Adverse Event” checked or lists a solicited AE that has “Caused Study Termination” checked that is at least Grade 1 or an unsolicited AE that has “Caused Study Discontinuation” checked that is at least Grade 1 or missing and is within the time period indicated.
- System Organ Class (SOC)/Preferred Term (PT) table: A solicited AE that has “Caused Study Termination” checked that is at least Grade 1 or an unsolicited AE that has “Caused Study Discontinuation” checked that is at least Grade 1 or missing and is within the time period indicated.

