4.3.2.2 Safety Endpoints

The observational endpoints for the evaluation of safety are:

- Occurrence, nature (Medical Dictionary for Regulatory Activities [MedDRA] preferred term), duration, intensity, relationship to vaccination, and whether the event led to early termination from the study, of any unsolicited systemic AEs reported in the 30 minutes after each vaccination
- Occurrence, time of onset, number of days of occurrence, intensity, action taken, and whether the reaction led to early termination from the study, of solicited (prelisted in the subject's diary card and CRF) injection site reactions occurring up to D07 after each vaccination
- Occurrence, time of onset, number of days of occurrence, intensity, action taken, and whether the reaction led to early termination from the study, of solicited (prelisted in the subject's diary card and CRF) systemic reactions occurring up to D07 after each vaccination
- Occurrence, nature (MedDRA preferred term), time of onset, duration, intensity, action taken, relationship to vaccination, and whether the event led to early termination from the study, of unsolicited AEs up to D30 after each vaccination
- Occurrence, nature (MedDRA preferred term), time of onset, duration, seriousness criteria, relationship to vaccination, outcome, and whether the event led to early termination from the study, of SAEs (including AESIs) throughout the trial from D0 to the last study visit

Assessment Methods

At each vaccination visit, the Investigator or a delegate will perform a physical examination on the basis of relevant medical history according to the Investigator's clinical judgment and will ask the parent / guardian about any solicited reactions and unsolicited AEs recorded in the diary card, as well as about any other AEs that may have occurred since the previous visit. All relevant data will be transcribed into the CRB according to the instructions provided by the Sponsor.

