5.2.3 Safety Analysis Set

The safety analysis set (SafAS) is defined as those subjects who have received at least 1 dose of the study vaccine and have any safety data available.

All subjects will have their safety analyzed after each dose according to the vaccine they actually received at that dose. For ‘any dose’ safety analyses, all subjects will have their safety analyzed according to the vaccine received at the first dose.

Safety data recorded for a vaccine received out of protocol design will be excluded from the analysis (and listed separately).

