5.2.4 Populations Used in Analyses

All immunogenicity analyses will be performed on the Per-Protocol Analysis Set (PPAS) including PPAS1 and PPAS2. Additional immunogenicity analyses will be performed for exploratory purposes on the Full Analysis Set (FAS), including FAS1 and FAS2, according to randomization group. All safety analyses will be performed on the Safety Analysis Set (SafAS and SafAS1 – SafAS6).

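### The completion-form criterion for AE terminations is tied to no dose or period, so a per-dose safety overview may count one termination after every dose the child received

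*SAP*

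**What the plan says.** SAP 4.4.1.5.5 opens its list of rules with "In general, the items that are counted are". For the safety overview table it offers three alternatives, any one of which is enough:

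1. the end-of-study form gives Adverse Event as the participant's status ("A participant who has either on the “Completion at End of Study” form, question “What was the participant's status?” has “Adverse Event” checked");
2. a solicited reaction of Grade 1 or higher is marked as having caused termination;
3. an unsolicited AE is marked as having caused discontinuation and is "at least Grade 1 or missing and is within the time period indicated".

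The rule for the SOC/PT table in the same section uses only the two AE-level alternatives and ends in the same way: "checked that is at least Grade 1 or missing and is within the time period indicated". The disposition rule uses only the form status.

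On where safety is analysed, SAP 5.2.3 states: "All subjects will have their safety analyzed after each dose according to the vaccine they actually received at that dose". SAP 5.2.4 adds: "All safety analyses will be performed on the Safety Analysis Set (SafAS and SafAS1 – SafAS6". Among the endpoints in SAP 4.3.2.2 is the occurrence of unsolicited AEs, "and whether the event led to early termination from the study, of unsolicited AEs up to D30 after each vaccination". SAP 4.4.1.2.4 leaves unsolicited AEs with onset after the 30-day window out of the analysis and lists them separately.

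**The concern.** The form status is recorded once per child, at the end of participation. A child who leaves for an AE after the third vaccination visit has that status whichever dose is being tabulated. Membership of a per-dose set (SAP 5.2.3.2 to 5.2.3.7) requires only receipt of vaccine at that visit and some safety data, so the child stays in the sets for the first two visits as well. Applied as worded, the overview for each earlier dose would show a termination that came after a later one.

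Early termination is a named component of the safety endpoints, and safety here is purely descriptive (SAP 5.1.3), so these counts are themselves the result. The distortion also blurs which visits carry the terminations. In Group 3 only Prevnar 13 is given at Visit 1, and MenACYW is given at Visits 2, 4 and 6 (SAP Table 3.2). A child who leaves after a MenACYW visit would also appear as a termination after the Prevnar-only visit. A child who leaves after routine-only Visit 3 would also appear after the first MenACYW dose.

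The SOC/PT table, which relies on AE flags and the window, would count the same child once or not at all.

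**Working it through.** The plan gives no figure for this rule, so there is none to reproduce. The check has two parts: how the sentence reads, and what it yields when counted.

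**Reading the sentence.** The window phrase follows the grade condition inside the clause on unsolicited AEs. In the SOC/PT rule the same words can only describe AEs, because no form status appears there. The natural reading is therefore that the form alternative has no window. If the phrase is taken to govern all three alternatives, the form status must be tested against a post-dose period, yet the SAP gives no date, dose or linking rule for it. Protocol 5.2.10 defines the category at subject level, and Protocol 5.2.8 also assigns it to voluntary withdrawals made for safety concerns. Both readings leave something to specify.

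**Inputs.** Vaccination visits: 4 in Groups 1 and 2, 5 in Groups 3 and 4 (SAP Tables 3.3 to 3.6). Planned group sizes: 200, 100, 150 and 75 (Protocol 6.5). Assumptions: the child was vaccinated and has safety data at every visit up to visit k, leaves for an AE after visit k, and the overview is tabulated on SafAS1 to SafAS6.

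**Entries per termination.** Form alternative without a window: k. Tied to the window: at most 1. Surplus: at least k − 1.

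| Last vaccination visit before the event | Entries as worded | Entries if time-limited | Surplus |
|---|---|---|---|
| 1 | 1 | at most 1 | at least 0 |
| 2 | 2 | at most 1 | at least 1 |
| 3 | 3 | at most 1 | at least 2 |
| 4 (last in Mexico) | 4 | at most 1 | at least 3 |
| 5 (Russian Federation only) | 5 | at most 1 | at least 4 |

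One in-window termination after each visit would give 1+2+3+4 = 10 entries instead of 4 in Mexico, and 1+2+3+4+5 = 15 instead of 5 in the Russian Federation.

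**Size of one surplus entry**, at full planned group size (100/n, Clopper-Pearson 95% CI):

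| Group | n | Correct: 0/n | With one surplus entry: 1/n |
|---|---|---|---|
| 1 | 200 | 0% (0 to 1.83) | 0.50% (0.01 to 2.75) |
| 2 | 100 | 0% (0 to 3.62) | 1.00% (0.03 to 5.45) |
| 3 | 150 | 0% (0 to 2.43) | 0.67% (0.02 to 3.66) |
| 4 | 75 | 0% (0 to 4.80) | 1.33% (0.03 to 7.21) |

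**Onset beyond D30.** Take a child whose event starts more than 30 days after the 6-month dose and before the 12-month dose. The time-limited count is 0 in every 30-day table. As worded, the form status gives 3 entries in Mexico (Visits 1 to 3) and 4 in the Russian Federation (Visits 1 to 4). This goes against the exclusion in SAP 4.4.1.2.4 and would disagree with the SOC/PT table. A 30-day any-dose overview, if one is produced, would show 1 instead of 0.

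**Tables not affected.** In the whole-study overview on the overall SafAS, and in the disposition table, the child is counted once, correctly.

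**The case against.** The strongest objection is that no sentence or table shell says the safety overview is tabulated by dose. The only explicit remark on its layout, in SAP 5.1.4.2, concerns race and gender. The sections on analysis sets speak of safety analyses collectively, and they include the overall set, where nothing is inflated. This stands: the per-dose overview is an inference, though a well-founded one, since the rule itself refers to an indicated period.

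Second, the sentence ends with a window that could be read to cover all three alternatives, and the list is introduced as general. This also stands in part: absence of a window is the likelier reading, not the only one. It does not remove the problem, because no alternative rule is supplied and the form status cannot be placed in a window without one.

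Third, SAEs and AESIs are followed to the last visit and analysed over the whole study as well as within 7 and 30 days (SAP 4.4.1.3, 4.4.1.4). A late termination is therefore not wrong in every table. That is right: the zero count applies only to 30-day tables.

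Fourth, the form status has a purpose. It catches a child whose termination was never linked to a flagged AE, and Protocol 11.2 already provides for data queries. A difference between the overview and the SOC/PT table is then not in itself an error. That argues for keeping the status where it fits, in the whole-study table, and for handling unflagged cases explicitly.

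A reader might infer that the plan certainly counts each termination after every dose, or that total AE terminations will be overstated. The documents support neither: the first rests on a layout that is not stated, and the whole-study counts are correct.

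**Conclusion.** The point holds in conditional form. The form alternative is a whole-study status tied to no dose and, on the natural reading, to no period. If the overview is produced on SafAS1 to SafAS6, as SAP 5.2.3 and 5.2.4 imply, one AE termination may be entered up to 4 times in Mexico and up to 5 times in the Russian Federation, against at most 1. The wrong entries are those for doses earlier than the last one before the event, and those in 30-day tables for events starting after D30.

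The effect is small: per termination, one child in each affected table, 0.5 to 1.33 percentage points at planned group size. The number of AE terminations is not given in the documents. It is assumed small, for example 1 to 5 of 525. Average multipliers of 2.5 (Mexico) and 3.0 (Russian Federation) follow only if terminations are spread evenly over visits, which is an assumption and should not be read as expected inflation. No immunogenicity result, analysis-set denominator or primary conclusion is touched. It still merits correction, because the stated rule can yield a wrong count on a named safety endpoint and is cheap to repair.

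**What to change.** Amend SAP 4.4.1.5.5 as follows:

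- **Per-dose or time-windowed overviews:** count a participant only through an AE flagged as causing discontinuation whose onset lies in the indicated period after that dose, as in the SOC/PT rule.
- **Whole-study overview on the overall SafAS:** retain the completion-form alternative here only.
- **Form says Adverse Event but no AE is flagged:** query before database lock. If unresolved, assign the termination once, to the last vaccination before it.

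The SAP should also say whether the overview is produced by dose. The cost is a short addition to the SAP and a small change to the overview program, with no new data. The downside is the query or assignment step for unflagged cases.

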4.4.2 Immunogenicity

4.4.2.1 Computed Values at a specific Blood Sample

In order to appropriately manage extreme values (undetectable responses $<$ the lower limit of quantitation [LLOQ] and \geq the upper limit of quantitation [ULOQ]) for analysis purposes, the following computational rule is applied to the values provided in the clinical database for each blood sample drawn:

- If a value is $<$ LLOQ, then use the computed value LLOQ/2
- If a value is between \geq LLOQ and $<$ ULOQ, then use the value
- If a value is \geq ULOQ, then use the computed value ULOQ

4.4.2.2 Seroprotection

hSBA vaccine seroprotection is defined as: hSBA titers \geq 1:8.

4.4.2.3 Fold-rise

The derived endpoint fold-rise is driven by both baseline and post-baseline computed values and is computed as follows. Generally, for extreme values, this algorithm minimizes the numerator and maximizes the denominator.

- If the baseline computed value is $<$ LLOQ and the post-baseline computed value is $<$ LLOQ, then the fold-rise is 1
- If the baseline computed value is \geq LLOQ and the post-baseline computed value is \geq LLOQ, then the fold-rise is post-baseline computed value / baseline computed value
- If the baseline computed value is \geq LLOQ and the post-baseline computed value is $<$ LLOQ, then the fold-rise is (LLOQ/2) / baseline computed value
- If the baseline computed value is $<$ LLOQ and the post-baseline computed value is \geq LLOQ, then the fold-rise is post-baseline computed value /LLOQ

Note: If baseline or post-baseline is missing, then fold-rise is missing.

4.4.2.4 A/C/Y/W Vaccine Seroresponse

hSBA vaccine seroresponse for serogroups A, C, Y, and W is defined as either:

- Post-vaccination hSBA titers \geq 1:16, if pre-vaccination hSBA titers $<$ 1:8 or
- At least a 4-fold increase in hSBA titers from pre- to post-vaccination, if pre-vaccination hSBA titers \geq 1:8.

4.4.3 Derived Other Variables

4.4.3.1 Age for Demographics

The age of a subject in the study was the calendar age in day at the time of inclusion.

4.4.3.2 Subject Duration

The duration of a subject in the study is computed as follows: Maximum (date of last visit, date of term form) – (date of Visit 1) +1.

The duration of a subject in the study including follow-up is computed as follows: Maximum (date of last visit, date of term form, last date of follow-up contact) – (date of Visit 1) +1.

4.4.3.3 Duration of the Study

The duration of the study (until last visit) is computed as follows: Maximum of all subjects (date of last visit, date of termination form) – minimum for all subjects (date of Visit 1) +1.

The duration of the study (including follow-up) is computed as follows: Maximum of all subjects (date of last visit, date of termination form, date of last follow-up contact) – minimum for all subjects (date of visit V01) +1

5 Statistical Methods and Determination of Sample Size

The statistical analyses will be performed under the responsibility of the Sponsor's Biostatistics platform using SAS[®] Version 9.4 software or later.

The results of the statistical analysis will be available in the final clinical study report (CSR).

The CI for the single proportion will be calculated using the exact binomial method (Clopper-Pearson method, quoted by Newcombe (1), i.e., using the inverse of the beta integral with SAS[®]).

For immunogenicity and efficacy results, assuming that Log10 transformation of the titers / data follows a normal distribution, at first, the mean and the 95% CI will be calculated on Log10 (titers / data) using the usual calculation for normal distribution (using Student's t distribution with n-1 degree of freedom), then antilog transformations will be applied to the results of calculations, in order to provide geometric means (GMs) and their 95% CI.

For descriptive purposes, the following statistics will be presented:

-
- Confidential/Proprietary Information
 - Page 54 of 67

Table 5.1: Descriptive statistics produced

Baseline characteristics and follow-up description	Categorical data	Number of subjects. Percentage of subjects.
	Continuous data	Mean, standard deviation, quartiles, minimum, and maximum.
Clinical safety results	Categorical data	Solicited: Number and percentage (95% CIs) of subjects. Unsolicited: Number and percentage (95% CIs) of subjects, and number of events.
Immunogenicity results	Categorical data (seroprotection, seroconversion, cutoff)	Number and percentage (95% CIs) of subjects.
	Continuous data (titer / data†)	Log10: Mean and standard deviation. Anti-Log10 (work on Log10 distribution, and anti-Log10 applied): Geometric mean, 95% CI of the geometric mean, quartiles, minimum, and maximum. Graphical representation by Reverse Cumulative Distribution Curve (RCDC).

5.1 Statistical Methods

5.1.1 Hypotheses and Statistical Methods for Primary Objective

5.1.1.1 Hypotheses

No hypotheses will be tested. Descriptive statistics will be presented.

5.1.1.2 Statistical Methods

Descriptive analyses on meningococcal serogroups A, C, Y, and W measured by hSBA for Groups 1, 2, and 3, 30 days after the last vaccination in the second year

-
- Confidential/Proprietary Information
 - Page 55 of 67

of life with MenACYW conjugate vaccine or Menveo[®] will be computed on the following parameter:

- Percentage of subjects with titer $\geq 1:8$ and 95% CI

The 95% CI will be computed using the exact binomial distribution (Clopper-Pearson method).

5.1.2 Hypotheses and Statistical Methods for Secondary Objective

5.1.2.1 Hypotheses

No hypotheses will be tested. Descriptive statistics will be presented.

5.1.2.1.1 Statistical Methods for Secondary Objectives 1, 2 and 4

Descriptive analyses on meningococcal serogroups A, C, Y, and W measured by hSBA, for Groups 1, 2, and 3, before the first vaccination, 30 days after the last vaccination of the infant series with MenACYW conjugate vaccine or Menveo[®] (2nd dose of MenACYW conjugate vaccine and 3rd dose of Menveo[®]) and 30 days after the last vaccination in the second year of life will include but not limited to the following:

- GMT and 95% CI
- Titer distribution and RCDCs
- Percentage of subjects with titer $\geq 1:4$ and $\geq 1:8$ and 95% CI
- Percentage of subjects with titer ≥ 4 -fold rise from pre-vaccination to post-infant vaccination, and 95% CI
- Percentage of subjects with titer ≥ 4 -fold rise from pre-vaccination to post-12-month vaccination, and 95% CI
- Percentage of subjects with hSBA vaccine seroresponse^a and 95% CI

In general, categorical variables will be summarized and presented by frequency counts, percentages, and CIs. The 95% CIs of point estimates will be calculated using the normal approximation for quantitative data and the exact binomial distribution (Clopper-Pearson method) for proportions. For GMTs and geometric mean concentrations (GMCs), 95% CIs of point estimates will be calculated using a normal approximation assuming they are log-normally distributed.

5.1.2.1.2 Statistical Methods for Secondary Objectives 5, 6, 7, 8

Descriptive analysis on meningococcal serogroups A, C, Y, and W measured by rSBA before the first vaccination, 30 days after the last vaccination of the infant

-
- Confidential/Proprietary Information
 - Page 56 of 67

series (2nd dose of the MenACYW conjugate vaccine and 3rd dose of Menveo[®]), and 30 days after the last vaccination of the second year of life with MenACYW conjugate vaccine or Menveo[®] in a subset of subjects (100 subjects per group in Groups 1 and 3, and 50 subjects in Group 2) will include but not limited to the following parameters:

- GMT and 95% CI
- Titer distribution and RCDCs
- Percentage of subjects with titer $\geq 1:8$ and $\geq 1:128$ and 95% CI
- Percentage of subjects with titer ≥ 4 -fold rise from pre-vaccination to post-vaccination, and 95% CI
- Percentage of subjects with rSBA vaccine seroresponse and 95% CI

5.1.2.1.3 Statistical Methods for Secondary Objective 3

The analyses on the concomitant vaccines will include GMT and titer distribution or GMC, and RCDC, as well as percentage of subjects with:

The Russian Federation^a:

- 30 days after vaccination with MMR vaccine at 12 months of age
 - Anti-measles antibody concentrations (serostatus cutoff: 255: mIU/mL).
 - Anti-mumps antibody concentrations (serostatus cutoff: 10 Mumps ab units/mL).
 - Anti-rubella antibody concentrations (serostatus cutoff: 10 IU/mL).
- Before the first vaccination with Pentaxim[®]
 - Anti-pertussis (PT and FHA) antibody concentrations
- 30 days after the last vaccination with Pentaxim[®] at 6 months of age:
 - Anti-tetanus antibody concentrations ≥ 0.1 IU / mL and 1.0 IU / mL
 - Anti-diphtheria antibody concentrations ≥ 0.1 IU / mL and 1.0 IU / mL

^a Anti-pneumococcal antibody concentrations will not be determined in this study for the Russian Federation.

- Anti-pertussis (PT and FHA) antibody concentrations (vaccine response)
- Anti-poliovirus types 1, 2, and 3 antibody titers $\geq 1:8$
- Anti-PRP antibody concentrations and $\geq 0.15 \mu\text{g} / \text{mL}$ and $1.0 \mu\text{g} / \text{mL}$
- 30 days after vaccination with ENGERIX-B^{®a} at 6 months of age
 - Anti-HBs antigen concentrations $\geq 10 \text{ mIU} / \text{mL}$ and $\geq 100 \text{ mIU} / \text{mL}$

Mexico:

- 30 days after vaccination with M-M-R^{®II} at 12 months of age
 - Anti-measles antibody concentrations (serostatus cutoff: 255 mIU/mL)
 - Anti-mumps antibody concentrations (serostatus cutoff: 10 Mumps Ab units/mL)
 - Anti-rubella antibody concentrations (serostatus cutoff: 10 IU/mL)
- 30 days after vaccination with Prevnar 13[®] at 6 months of age and the last vaccination with Prevnar 13[®] at 12 months of age
 - Anti-pneumococcal antibody concentrations $\geq 0.35 \mu\text{g}/\text{mL}$ and $1.0 \mu\text{g}/\text{mL}$ for serotypes 1, 3, 4, 5, 6A, 6B, 7F, 9V, 14, 18C, 19A, 19F, and 23F
- Before the first vaccination with Hexacima[®]
 - Anti-pertussis^b (PT and FHA) antibody concentrations
- 30 days after the last vaccination with Hexacima[®] vaccine at 12 months of age

^a In the event ENGERIX B[®] cannot be supplied in the Russian Federation, a locally licensed monovalent hepatitis B vaccine will be administered instead. Further details will be provided in the CSR.

^b Pertussis vaccine response is defined as:

- If the pre-vaccination concentration is $< 4 \times \text{LLOQ}$, then the post-vaccination concentration is $\geq 4 \times \text{LLOQ}$;
- If the pre-vaccination concentration is $\geq 4 \times \text{LLOQ}$, then the post vaccination concentration is \geq the pre-vaccination concentration

- Anti-tetanus antibody concentrations ≥ 0.1 IU/mL and 1.0 IU/mL
 - Anti-diphtheria antibody concentrations ≥ 0.1 IU / mL and 1.0 IU / mL
 - Anti-pertussis (PT and FHA) antibody concentrations and pertussis vaccine response
 - Anti-poliovirus types 1, 2, and 3 antibody titers $\geq 1:8$
 - Anti-PRP antibody concentrations and ≥ 0.15 μg / mL and 1.0 μg / mL
 - Anti-HBs antigen concentrations ≥ 10 mIU / mL and ≥ 100 mIU / mL
- Before the first vaccination and 30 days after the last vaccination with RotaTeq[®] at 6 months of age
 - Anti-RV IgA ≥ 3 -fold and ≥ 4 -fold antibody titers from baseline to 30 days after last dose

